10.3. Statistical Analysis

The PK Analysis Subset will be used for statistical analyses of plasma and urine PK parameters described above.

10.3.1. Assessment of Dose Proportionality

The presence of dose proportionality in plasma in terms of exposure parameters (C_{max}, AUC_{0-last}, and AUC_{0-inf}) over the range of studied doses will be assessed among the Fasted Dose Groups using a power model approach with methods described by Smith et al. [5] The PK Analysis Subset will be used for this analysis.

The power model for the specific case of AUC_{0-last} may be specified with model parameters α and β to be estimated as:

$$AUC_{0-last} = e^\alpha \times dose^\beta$$

Let ρ be the highest dose studied / lowest dose studied and let (L, U) represent the 90% CI for β . In the presence of dose proportionality, $\rho^{\hat{\beta}}/\rho = \rho^{\hat{\beta}-1} = 1$. Note that normality of $\hat{\beta}$ is assumed, and this assumption implies that $\rho^{\hat{\beta}-1}$ has an assumed log-normal distribution. Accordingly, dose proportionality across the studied dose range is concluded using methodology analogous to that commonly used for an assessment of bioequivalence when:

$$\Theta_1 = 0.8 \leq \rho^{L-1} < \rho^{U-1} \leq 1.25 = \Theta_h.$$

Or, equivalently,

$$1 + \frac{\log 0.8}{\log \rho} \leq L < U \leq 1 + \frac{\log 1.25}{\log \rho}.$$

The analysis may be inconclusive if the CI (ρ^{L-1}, ρ^{U-1}) overlaps partially with the interval (0.80, 1.25) or if the (ρ^{L-1}, ρ^{U-1}) contains the interval (0.80, 1.25).

If graphical evidence suggests dose proportionality may exist over a subset of the dose range, the above criteria of Smith et al [5]. may be applied to a subset of the data only containing values for subjects within a limited dose range. If lack of dose proportionality is evident for higher doses, other dose proportionality analyses using a subset of the full dose range studied may be explored.

Dose proportionality assessments will be presented graphically and tabularly:

- Tabular results of statistics and parameters from the plasma dose proportionality power model will be presented for both VT-1598 and VT-11134 in [Table 101](#).
- Predicted values from a power model, including 90% pointwise prediction bands, will be overlaid on plots of the exposure parameter parameters (C_{max}, AUC_{0-last}, or AUC_{0-inf}) versus dose. Pointwise prediction bands will be defined by lower and upper limits of 90% pointwise prediction intervals

computed from the power model at each planned level dose level. Figures will be presented for all exposure parameters. For VT-1598, C_{max} will be presented in [Figure 101](#), AUC_{0-last} in [Figure 102](#), and AUC_{0-inf} in [Figure 103](#). For VT-11134, C_{max} will be presented in [Figure 104](#), AUC_{0-last} in [Figure 105](#), AUC_{0-inf} in [Figure 106](#).

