2.1. Purpose of the Analyses

This SAP describes safety and PK analyses of 40 mg, 80 mg, 160 mg, 320 mg, and 640 mg of VT-1598 given orally under a fasted state; and of 160 mg of VT-1598 given orally under a fed state (after administration of a high-fat, high calorie meal). PK analyses include assessment of VT-1598 and its primary metabolite, VT-11134.

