5. SAMPLE SIZE CONSIDERATIONS

This is a Phase 1 FIH study to assess the safety and PK of VT-1598. Since the study is primarily aimed at safety and PK evaluation, no formal power calculations based on testing a statistical hypothesis were constructed. The sample size of 8 subjects (6 subjects receiving VT-1598 and 2 subjects receiving placebo) per cohort is based on clinical experience and judgement and should provide adequate clinical information to meet the study objectives. The comparisons of PK between the fasted and fed cohorts (Cohort 3 and Cohort 6) are exploratory rather than formal analyses of fed bioequivalence. Fasted and fed PK profiles from 6 subjects are sufficient to meet the intended purpose.

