Statistics	Inpatient Period (0-72 h) ^a		Nominal Collection Time Interval ^a							
	A _e _{last} (mg)	CL _R (mL/min)	A _e ₀₋₆ (mg)	A _e ₆₋₁₂ (mg)	A _e ₁₂₋₂₄ (mg)	A _e ₂₄₋₃₆ (mg)	A _e ₃₆₋₄₈ (mg)	A _e ₄₈₋₆₀ (mg)	A _e ₆₀₋₇₂ (mg)	
N	x	x	x	x	x	x	x	x	x	
Mean	x	x	x	x	x	x	x	x	x	
SD	x	x	x	x	x	x	x	x	x	
Min	x	x	x	x	x	x	x	x	x	
Max	x	x	x	x	x	x	x	x	x	
CV %	x	x	x	x	x	x	x	x	x	
GM	x	x	x	x	x	x	x	x	x	

^a Times are relative to time of dosing.

Table 96: Summary Statistics for VT-11134 PK Parameters in Urine, 80 mg Fasted Dose Group

This table will repeat Table 95 for VT-11134 PK parameters in Urine for the 80 mg Fasted Dose Group

Table 97: Summary Statistics for VT-11134 PK Parameters in Urine, 160 mg Fasted Dose Group

This table will repeat Table 95 for VT-11134 PK parameters in Urine for the 160 mg Fasted Dose Group

Table 98: Summary Statistics for VT-11134 PK Parameters in Urine, 160 mg Fed Dose Group

This table will repeat Table 95 for VT-11134 PK parameters in Urine for the 160 mg Fed Dose Group

Table 99: Summary Statistics for VT-11134 PK Parameters in Urine, 320 mg Fasted Dose Group

This table will repeat Table 95 for VT-11134 PK parameters in Urine for the 320 mg Fasted Dose Group

Table 100: Summary Statistics for VT-11134 PK Parameters in Urine, 640 mg Fasted Dose Group

This table will repeat Table 95 for VT-11134 PK parameters in Urine for the 640 mg Fasted Dose Group

Table 101: Assessment of Dose Proportionality Among Fasted Dose Groups

Statistic	VT-1598			VT-11134		
	C _{max}	AUC _{0-last}	AUC _{0-inf}	C _{max}	AUC _{0-last}	AUC _{0-inf}
	(ng/mL)	(ng*h/mL)	(ng*h/mL)	(ng/mL)	(ng*h/mL)	(ng*h/mL)
Lowest Dose Included (mg)	x	x	x	x	x	x
Highest Dose Included (mg)	x	x	x	x	x	x
ρ	x	x	x	x	x	x
β -hat	x.XXX	x.XXX	x.XXX	x.XXX	x.XXX	x.XXX
Standard Error (β -hat)	x.XXX	x.XXX	x.XXX	x.XXX	x.XXX	x.XXX
$\rho^{\beta\text{-hat}-1}$ 90% CI	(x.xx, x.xx)	(x.xx, x.xx)	(x.xx, x.xx)	(x.xx, x.xx)	(x.xx, x.xx)	(x.xx, x.xx)
Conclude parameter shows dose proportionality?	Yes/No	Yes/No	Yes/No	Yes/No	Yes/No	Yes/No

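### Table 101 prints an imprecise dose-proportionality result as No, and with 6 subjects per dose the 0.80–1.25 rule cannot be met above an estimated residual CV of about 26%

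*SAP*

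**What the plan says.** Dose proportionality for Cmax, AUC0-last and AUC0-inf "will be assessed among the Fasted Dose Groups using a power model approach" (SAP 10.3.1). With ρ the ratio of highest to lowest dose, proportionality is concluded if the 90% CI of ρ^(β−1) lies within 0.80–1.25; the SAP describes this by saying that "dose proportionality across the studied dose range is concluded using methodology analogous to that commonly used for an assessment of bioequivalence".

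The same section gives two further outcomes. The analysis may be inconclusive if the CI "overlaps partially with the interval (0.80, 1.25") or contains that interval. And "If graphical evidence suggests dose proportionality may exist over a subset of the dose range", the same criterion may be applied to a limited dose range.

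Table 101 (SAP Appendix 1) reports, for three parameters and two analytes, ρ, the slope estimate, its standard error and the 90% CI of ρ^(β−1). Its last row is "Conclude parameter shows dose proportionality", and the only entries offered are Yes and No.

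The number of subjects is not derived from this analysis. "The sample size of 8 subjects (6 subjects receiving VT-1598 and 2 subjects receiving placebo) per cohort" rests on clinical experience, and no power calculation was made (SAP 5).

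**The concern.** The limits are those of a bioequivalence assessment, but they are applied to a between-subject comparison of 30 people over a 16-fold range. If the CI is wide by design, the rule can fail for a drug that is exactly proportional. The decision row then has no entry for that case. A reader of the report would see No and could take lack of precision for evidence of non-proportionality. The distinction matters here because animal exposure rose less than in proportion to dose (protocol 2.1, Pharmacokinetics), so a No would look like confirmation. The table holds six such entries.

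**Working it through.** The documents state no power or CV for this analysis, so there is no planned figure to reproduce.

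**Inputs**
- Doses: "safety and PK analyses of 40 mg, 80 mg, 160 mg, 320 mg, and 640 mg of VT-1598 given orally under a fasted state" (SAP 2.1), so ρ = 640/40 = 16 and ln ρ = 2.773.
- Six active subjects per fasted dose, different people at each dose: 30 subjects, 28 residual df.
- 90% CI and limits 0.80–1.25 (SAP 10.3.1); ln 1.25 = 0.2231.
- CV = √(exp(s²) − 1) (SAP 10.2), with s the residual SD on the log scale.
- Model: log exposure on log dose, as in the power model of 10.3.1. (The Table 101 footnote prints dose where log dose is needed.)
- Between-subject CV: not given. It is an assumption, shown over a range.

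**Limits on β.** 1 ± 0.2231/2.773 = 1 ± 0.0805, so the CI for β must lie within 0.9195–1.0805.

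**Precision.** SE(β) = s/√Sxx, with Sxx = 6 × (ln 2)² × 10 = 28.83 and √Sxx = 5.369. With t(0.95, 28) = 1.701, the half-width is 1.701 × s/5.369.

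**Ceiling.** At an estimated slope of exactly 1 the rule needs s ≤ 0.0805 × 5.369/1.701 = 0.254, that is CV ≤ 25.8%. Any other slope estimate makes it harder.

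The same calculation for adjacent doses:

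| Doses | ρ | Limit on half-width | √Sxx | t | Largest s | CV ceiling |
|---|---|---|---|---|---|---|
| 5 | 16 | 0.0805 | 5.369 | 1.701 | 0.254 | 25.8% |
| 4 | 8 | 0.1073 | 3.797 | 1.717 | 0.237 | 24.1% |
| 3 | 4 | 0.1610 | 2.401 | 1.746 | 0.221 | 22.4% |
| 2 | 2 | 0.3219 | 1.201 | 1.812 | 0.213 | 21.6% |

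Narrowing the range removes subjects and dose spread faster than it relaxes the limits on β. For AUC0-inf, values with more than 20% extrapolation are dropped (SAP 10.2). With 5 or 4 evaluable subjects per dose the full-range ceiling is 23.3% or 20.6%.

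**Chance of meeting the rule when true β = 1** (numerical integration, checked by simulation):

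| True CV | 5 doses | 4 | 3 | 2 |
|---|---|---|---|---|
| 15% | 76% | 68% | 60% | 56% |
| 20% | 37% | 28% | 21% | 20% |
| 25% | 10% | 6% | 5% | 6% |
| 30% | 1.6% | 1.0% | 0.9% | 1.7% |

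An 80% chance over the full range needs a true CV of 14.5% or less. At a true CV of 30%, 100 − 1.6 = 98.4% of exactly proportional results would not earn a Yes.

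**What the same data can support.** Because ln 0.8 = −ln 1.25, the SAP's inequality holds for every dose ratio up to exp(ln 1.25/max(1 − L, U − 1)), where (L, U) is the 90% CI for β. At an estimated slope of 1 and CV 30%, s = √ln(1.09) = 0.2936, the half-width is 1.701 × 0.2936/5.369 = 0.0930, and the ratio is exp(0.2231/0.0930) ≈ 11. At CV 40% and 50% it is about 6.2 and 4.4. These are best cases. Allowing for sampling error in the slope, the medians when true β = 1 are about 5.6-, 3.7- and 2.9-fold at CV 30%, 40% and 50%.

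**When exposure departs at the top.** Suppose exposure is proportional to 320 mg and then flat to 640 mg, with CV 15%. The full range passes 0% of the time and the 40–320 mg subset about 68%. The slope fitted to all doses averages 0.80 and the largest-ratio figure has a median of about 2.2, although exposure is exactly proportional over 8-fold. With a true slope of 0.95 and CV 15%, five doses pass 28% of the time and three doses 47%.

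**The case against.** Much of what a reviewer would ask for is already there. Table 101 gives the slope, its standard error and the CI of ρ^(β−1), and Figures 101–106 add fitted curves with 90% prediction bands. The text of 10.3.1 recognises an inconclusive outcome, so a wide CI is not a finding of non-proportionality under the SAP. Read literally, No in Table 101 means only that proportionality was not concluded. The trial tests no formal hypotheses (protocol 10.1), the analysis serves a secondary PK objective, and no escalation decision depends on the row. All of this stands. It limits the point to reporting, but it does not supply the missing third entry.

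Three stronger readings are tempting and are not supported:

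- *The verdict is fixed in advance by the design.* That needs a human CV, and the documents give none. At a true CV of 10% the full-range rule passes 99% of the time, and at 15% it passes 76%.
- *No drug with a CV above 26% can pass.* The ceiling is exact for the estimated residual CV. At a true CV of 26% the chance is still about 7%, because the estimate can fall below the truth.
- *The subset step is useless and should go.* It does not cure imprecision, but it is meant for a departure at higher doses, and there it helps, as the plateau example shows.

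**Conclusion.** The point holds as one about precision and reporting. With 6 active subjects per fasted dose and ρ = 16, the rule cannot be met above an estimated residual CV of about 26%, and it becomes unlikely well below that: 37% at a true CV of 20% for an exactly proportional drug. Table 101 then turns an outcome that 10.3.1 would call inconclusive into No. Whether this happens depends on the actual CV, which cannot be judged from the documents. The figures assume a log-linear model with constant variance and six evaluable subjects per dose; fewer make the rule harder to meet. With no formal hypothesis at stake, this is a risk of misreading, not of an inflated error rate.

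**What to change.** 1. In Table 101 replace Yes/No with Yes, Inconclusive and No, following 10.3.1: Yes if the CI lies within 0.80–1.25, Inconclusive if it partly overlaps or contains that interval, No only if it lies wholly outside. Dropping the row would also do.
2. Add the 90% CI for β.
3. Add the largest dose ratio for which the SAP's inequality holds, exp(ln 1.25/max(1 − L, U − 1)). It draws a usable statement from all 30 subjects where the rule would give none.
4. Keep the subset analysis and label it exploratory. The ratio in item 3 assumes that one slope fits all doses and misleads if exposure plateaus, so it should be read beside the plots and the subset result and should not replace them.

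The cost is a revised table shell, a few sentences in 10.3.1 and a few lines of code. No new data are needed. The downside is slightly more reporting and a less simple verdict. If the change comes after the SAP is final, the clinical study report should describe and justify it, as the SAP preface requires of any deviation.

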10.3.2. Analysis of Change in T_{max} between Fasted and Fed Dose Groups

The difference in median T_{max} values and the corresponding 90% CI for the difference between the 160 mg Fasted Dose Group and Fed Dose Group will be estimated using the PK Analysis Subset. An exact Wilcoxon signed-rank test will be conducted to compare T_{max} between subjects who participated in both cohorts. This paired analysis will only be conducted if there are at least 3 individual subjects in the PK Analysis Population who are in Cohort 3 as well as Cohort 6. An exact Wilcoxon rank sum test will be used to compare the difference in median T_{max} between all subjects in the 160 mg Fasted Dose Group to the 160 mg Fed Dose Group, regardless of whether the subject participated in both dosing periods. Continuity corrections will not be used for either test. Results from the paired and unpaired comparison of changes in T_{max} will be presented in [Table 102](#).

10.3.3. Analysis of Exposure Parameter Ratios between Fasted and Fed Dose Groups

Exposure parameters (C_{max} , AUC_{0-last} , and AUC_{0-inf}), will be compared between the 160 mg Fasted and Fed Dose Groups using the PK Analysis Subset. The ratio of the GM of each parameter for the fed group compared to the GM of the same parameter in the corresponding fasted group will be estimated using a mixed effects model. Each exposure parameter will be estimated by fasting status with a random subject effect and a heterogeneous compound symmetry covariance structure. Because a random subject effect will be included, only one analysis will be conducted on all subjects in the 160 mg Fasted and 160 mg Fed Dose Groups for each exposure parameter, regardless of whether the subject participated in both dosing periods. In the event of nonconvergence of the model, first an unstructured covariance matrix will be specified. If the model still fails to converge the random subject effect will be removed from the model.

[Table 103](#) will display results comparing exposure parameters in both VT-1598 and VT-11134 between the 160 mg Fasted and 160 mg Fed Dose Groups, including the ratio estimate and a 90% CI.

Pseudo code to estimate the ratio of exposure parameters between the 160 mg Fasted and 160 mg Fed Dose Groups is presented below. Variables to be used in the model are also detailed below:

- FedCondition = indicator for dose received and fasting status; 160 mg Fed = 1, 160 mg Fasted = 2
- ExposureParam_LN = log transformed values of exposure parameters for each subject.

```
proc mixed data=data;
  class Subject_ID FedCondition;
  model ExposureParam_LN= Subject_ID FedCondition /DDFM=SATTERTH;
  random FedCondition /type=CSH sub= Subject_ID G;
  repeated /grp= FedCondition sub= Subject_ID;
  estimate 'Ratio of Fed to Fast' FedCondition 1 -1/CL alpha=0.1;
run;
```

Where `ExposureParam_LN` is the natural log of the exposure parameter being modeled (C_{max} , AUC_{0-last} , and AUC_{0-inf}) and `FedCondition` is a variable indicating the fed vs fasting condition. The `estimate` statement will give the mean of the natural log values of each exposure parameter and the associated 90% CIs on the log scale. Exponentiating the results of the `estimate` statement will give the GM and associated 90% CIs for each exposure parameter.

The resulting estimate from the mixed effects model will give the difference in log transformed values of the mean for each exposure parameter and the associated 90% CI on the log scale. These values will be exponentiated in order to present the ratio of the GM of exposure parameters and corresponding CIs on the original scale. This model and subsequent exponential transformation will be repeated for each exposure parameter (C_{max} , AUC_{0-last} , and AUC_{0-inf}). An absence of food effect will be indicated by the 90% CI being contained in the equivalence limits of 80-125 percent for C_{max} , AUC_{0-last} , and AUC_{0-inf} , per FDA guidance on the assessment of food effect [7].

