15. SUMMARY OF CHANGES IN THE CONDUCT OF THE STUDY OR PLANNED ANALYSES

Only one subject from the fasted 160 mg cohort (Cohort 3) returned for the fed 160 mg cohort (Cohort 6). This impacts the planned analysis of change in T_{max} between fasted and fed Dose Groups. Previously, an exact Wilcoxon-signed rank test had been proposed to compare subjects who had participated in both cohorts, however since fewer than 3 subjects were present in both cohorts, this analysis was not completed. Instead, only an exact Wilcoxon rank sum test was performed to compare the change in T_{max} between fasted and fed Dose Groups.

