^aN=Number of subjects with data used to compute the exposure parameters. Data was used from any subject in the PK Analysis Subset who received 160 mg VT-1598 under either a fasted or fed state, regardless of whether or not the subject participated in both study parts. BQL values were imputed as 0 if the sample was taken before the first measurable PK sample with a concentration above the LLOQ. BQL values were treated as missing otherwise.

^b90% CI estimated using a mixed effects model for the geometric mean of each parameter by fasting status with a random subject effect. Individual parameter estimates were log transformed before inclusion in the model.

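### The SAP 10.3.3 code fits subject as a fixed effect where the text says random; with one returning subject it gives no 90% CI for the food-effect rule

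*SAP*

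**What the plan says.** The prose of SAP 10.3.3 specifies fasting status as the factor of interest, subject as random and a heterogeneous compound symmetry (CSH) covariance. It relies on the random effect to pool paired and unpaired subjects: "Because a random subject effect will be included, only one analysis will be conducted on all subjects" in the two 160 mg groups. Footnote b of SAP Table 103 repeats this, describing the 90% CI as "estimated using a mixed effects model for the geometric mean of each parameter by fasting status with a random subject effect".

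The code under the same heading differs. Subject_ID is in the CLASS statement and on the MODEL line: "model ExposureParam_LN= Subject_ID FedCondition /DDFM=SATTERTH". Two covariance statements follow, "random FedCondition /type=CSH sub= Subject_ID G" and "repeated /grp= FedCondition sub= Subject_ID".

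There are two fallbacks: "In the event of nonconvergence of the model, first an unstructured covariance matrix will be specified", and then "If the model still fails to converge the random subject effect will be removed from the model". The section ends with the rule that a 90% CI lying inside 80–125% indicates no food effect.

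SAP Section 15 records what happened: "Only one subject from the fasted 160 mg cohort (Cohort 3) returned for the fed 160 mg cohort (Cohort 6"). It drops the paired Tmax test for that reason. It says nothing about the exposure ratios, and 10.3.3, its code and Table 103 are unchanged.

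**The concern.** The text and the code define different models, and a programmer cannot follow both. Had all six active subjects returned, the fixed-subject version would have been an ordinary paired analysis and the slip would have mattered little. With one returner, each unpaired subject's single value is absorbed by that subject's own parameter, so nothing is left from which to estimate variance.

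The effect of a high-fat meal on PK is a secondary objective (Protocol 3.2.2, SAP 3.1). Table 103 is the only planned output with a fed/fasted exposure ratio and CI, and 10.3.3 ties a stated conclusion to that CI. The model in the text avoids saturation but has its own gap: with one pair, the estimated within-subject correlation will often sit at its limit, and the SAP does not say whether such a fit counts as nonconvergence.

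**Working it through.** The SAP states no degrees of freedom, CV or power for this analysis, so there is no figure of its own to reproduce. Its `alpha=0.1` agrees with the 90% CI.

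**Inputs.** Six active subjects per cohort (SAP Table 1) and one subject in both cohorts (SAP Section 15). The number of evaluable fed profiles is not given, so 4 to 8 were tried.

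**Printed code: residual df.** Let m be the number of active subjects with both profiles, n the number of profiles and S the number of distinct subjects.

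- S = n − m
- rank of the fixed-effects matrix = S + 1 when m ≥ 1
- residual df = n − (S + 1) = m − 1

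With 6 + 6 profiles and m = 1: n = 12, S = 11, rank = 12, df = 0. With 6 fasted and 4, 5, 6, 7 or 8 fed, n and rank are both 10, 11, 12, 13 or 14, so df is 0 each time. With the planned m = 6: n = 12, S = 6, rank = 7, df = 5.

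For m = 1 the fed-minus-fasted estimate puts weights +1 and −1 on the returner's two values and 0 on all others. A different assumed covariance (GLS instead of OLS) gives the same estimate. With no error contrasts, REML has nothing from which to estimate a variance, so there is no valid standard error, Satterthwaite df or CI. If the returner was on placebo (Section 15 does not give the arm) or falls outside the PK Analysis Subset, then m = 0 and the contrast is not estimable.

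**Printed code: covariance.** Each subject has at most one value per condition, so the data carry three moments:

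- Var(fasted) = g1 + r1
- Var(fed) = g2 + r2
- Cov = ρ√(g1·g2)

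The RANDOM statement contributes g1, g2 and ρ, and the REPEATED statement r1 and r2. That is five parameters for three moments (Jacobian rank 3).

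**Fallbacks.** For two conditions an unstructured matrix has the same three parameters as CSH. It may help the optimiser but adds no information. Deleting only the RANDOM line leaves Subject_ID in MODEL and df at 0.

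**Text model.** With FedCondition as the only fixed effect, n = 12, rank = 2 and residual df = 10, so a CI exists. Its behaviour with one pair was simulated: log scale, 6 + 6 profiles, true ratio 1, CSH by REML, 3,000 runs per setting. The CVs are assumptions, and PROC MIXED itself was not run.

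| Between/within CV | Fits with \|ρ\| ≥ 0.99 | Coverage, boundary fits accepted (t10 / t5) | Boundary fits sent to Welch (t10 / Satterthwaite) | Welch alone | Median Welch CI factor |
|---|---|---|---|---|---|
| 30/20% | 73.1% | 55.7 / 58.5% | 90.6 / 92.3% | 91.6% | 1.43 |
| 40/20% | 75.4% | 51.7 / 54.8% | 91.1 / 92.8% | 92.2% | 1.56 |
| 50/30% | 73.6% | 55.6 / 58.3% | 91.0 / 92.9% | 92.2% | 1.76 |
| 60/30% | 76.4% | 52.7 / 55.7% | 91.6 / 92.9% | 92.5% | 1.90 |

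The t10, t5 and Satterthwaite labels refer to the df used for the mixed-model intervals. Interior fits alone covered 82–87% with t10 and 89–94% with Satterthwaite df.

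**What an unpaired CI can show.** The CI factor is exp(t(0.95, df)·σ·√(1/6 + 1/n_fed)), with σ = √ln(1 + CV²) and df = 4 + n_fed. Set the factor to 1.25 for an observed ratio of 1. With 6 fed, σ = 0.2231 / (1.8125 × 0.5774) = 0.2132, so CV = 21.6%. With 4 fed the limit is 18.8%, and with 8 fed 23.5%.

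**The case against.** The code is labelled pseudo code. The prose and the table footnote agree with each other, and an analyst who follows them gets a CI with 10 residual df. That is correct, and it confines the zero-df result to the printed code.

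The last fallback, read generously, removes the subject term altogether. What remains is fasting status with separate residual variances and Satterthwaite df, which is the Welch comparison. This is a fair reading, but it is not stated. The fallback is triggered only by nonconvergence, and it names a random effect while the term that causes the trouble is fixed.

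Section 15's silence is partly explained: the Tmax test had a minimum of three returners, whereas the exposure model was written for any overlap. That explains why no change was triggered. It does not make the result sound with a single pair.

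The 52–59% coverage figures use fixed df, while the SAP specifies Satterthwaite, and the 0.99 cut-off is a choice made for this check. They are therefore illustrative. The direction stands: in a separate check, boundary fits under-covered even with t on 1 df (about 74–77%).

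Making Welch the main analysis goes further than the minimum. By the figures above, a rule sending boundary fits to the unpaired comparison performs about as well. Finally, the comparison is exploratory (Protocol 10.2; SAP 4.2 and 5), and an unpaired ratio can be rebuilt from the geometric means, CVs and counts in SAP Tables 73–79. That limits the severity.

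**Conclusion.** The concern holds. The code contradicts the text on whether subject is fixed or random. With the single returner reported in Section 15, the printed model has 0 residual df whatever the number of fed profiles and cannot supply the interval that the 80–125% rule needs. This is algebra and rests on no assumed CV.

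The model in the text supplies an interval, but a sound one only if boundary fits go to the unpaired comparison. That part rests on simulation under assumed CVs and 6 + 6 evaluable profiles. It should be fixed. It is not critical, because no primary objective depends on Table 103 and the comparison is declared exploratory.

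**What to change.** 1. Make the code match the text. Take Subject_ID off MODEL and keep one identifiable covariance statement, for example `model ExposureParam_LN = FedCondition / ddfm=satterth;` with `repeated FedCondition / type=CSH subject=Subject_ID;`. Keep the ESTIMATE statement.
2. Make the unpaired log-scale comparison (Welch t, 90% CI) the main Table 103 analysis. It is in effect the SAP's own last fallback and matches the change already made for Tmax. Keep the model in step 1 as a sensitivity analysis, and state that a boundary correlation estimate (for example |ρ| ≥ 0.99) counts as nonconvergence.
3. Say in Section 15 and in the Table 103 footnote that the low return rate makes the exposure ratios a between-subject comparison, and that the choice rests on the number of returners, not on the exposure results.

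The cost is a few lines of code, a footnote and a sentence, with no new data. The interval will be wider, because it carries between-subject variance, and will rarely fit inside 80–125% (6 v 6 at an observed ratio of 1 needs a CV below about 22%). The change would also be recorded after the return count was known, which is why the reason in step 3 needs to be written down.
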